## Necrosis

Necrosis will be defined by enhancement of normal tissues as assessed by contrast-enhanced T1-weighted MR imaging, increased signal on T2 and FLAIR imaging, and the imaging parameters of apparent diffusion coefficient, fractional anisotropy, FDG-PET, and MR spectroscopy, when available. The gold standard to diagnose radiation necrosis has been biopsy; however, surgical intervention may increase morbidity, especially when considering the brainstem and cerebellum. Several imaging modalities have been investigated for their ability to diagnose necrosis and distinguish between necrosis and recurrent tumor. We will rely on serial changes, including increasing parenchymal enhancement on postcontrast T1 images and increasing volume of T2-weighted MR imaging signal abnormality and symptoms to grade necrosis according to the CTCAE v4.0. We have found that resolution of necrosis can be a long process during which lesions can show signs of improvement followed by progression in the same or other sites before stabilizing. According to the CTCAE v4.0 terminology, CNS necrosis has five grades: (1) asymptomatic; clinical or diagnostic observations only; intervention not indicated, (2) moderate symptoms; corticosteroids indicated, (3) severe symptoms; medical intervention indicated, (4) life-threatening consequences; urgent intervention indicated, (5) death. We anticipate that the rate of CNS necrosis (CTCAE v4.0 > grade 3) will be greater than 5% and less than 20% when estimated at one year. The lower bound of this estimate is based on our published data for patients treated in the primary setting [6, 137, 296]. The upper bound of this estimate is empiric. Asymptomatic patients with grade 1 necrosis referred for hyperbaric oxygen or other interventions to prevent progression of

> St. Jude Children's Research Hospital IRB NUMBER: Pro00004349

IRB Approval date: IRB APPROVAL DATE: 02/01/2023 imaging findings and the potential development of symptoms will be scored as grade 1 with supportive documentation.

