#### 8.0 REMOVAL FROM PROTOCOL AND OFF-STUDY CRITERIA

The survival for all participants will be followed on study until their death unless they or their parents request that no further information be made available to this study group.

For participants who are treated at collaborating institutions it is recommended that each patient to be taken off protocol be discussed with the PI of the study and if needed, pertinent studies should be sent to the PI for review.

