#### 8.1 **Off-Study Criteria**:

- Parent/Patient request
- Death
- PI discretion
- Lost to follow-up
- Protocol compliance
- Study completion
- Treatment with chemotherapy during the administration of radiation therapy
- Disease progression

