### **Historical Data and Analyses**

These analyses should be interpreted as exploratory and p-values are to be interpreted descriptively and are not adjusted for multiple comparisons. Patients with ependymoma who experience initial failure may be characterized based on their pattern of failure type (POF1 = local failure, POF2 = distant or POF3 = combined). We analyzed 50 patients previously retreated between 2000 and 2011 according to their retreatment strategy. Possible retreatment strategies include focal retreatment, which was used only for patients with local failures (RT2focal), and craniospinal irradiation with focal irradiation of the metastatic site(s) and primary site when indicated (RT2CSI). RT2CSI was used for all patients with combined or distant failure and selected patients with local only failure

> St. Jude Children's Research Hospital IRB NUMBER: Pro00004349

[figure not shown]
IRB Approval date: IRB APPROVAL DATE: 02/01/2023

Table 11.0 Pattern of Failure and Treatment Strategy for Historical Cohort

Retreatment Group	Initial Pattern of Failure	Retreatment Strategy	N
A	$POF_1 = local$	$RT_{2focal}$ = focal irradiation	22
В	$POF_1 = local$	$RT_{2CSI} = craniospinal irradiation$	7
C	POF 2 = distant	RT 2CSI	16
D	$POF_3 = local + distant$	RT 2CSI	5
Total			50

The following figure and table provide Kaplan-Meier estimates of the distributions of Progression-Free Survival and Overall Survival for the 50 patients in the historical cohort. PFS and OS are measured from the date of re-irradiation (RT2) until failure (relapse, disease progression, second malignancy or death) or death, respectively. Patients who have not failed are censored at their last date of contact.

Figure 11.1 Progression-free and Overall Survival Historical Cohort

St. Jude Children's Research Hospital IRB NUMBER: Pro00004349 IRB APPROVAL DATE: 02/01/2023

Rev. 3.2 dated: 1/19/2023 Protocol document date: 1/19/2023

Table 11.1 PFS and OS for the Historical Cohort

[figure not shown]
	PFS						OS					
Years Since	Risk	Fail	Cens	Prob	SE	Years Since	Risk	Fail	Cens	Prob	SE	
Iniatiation of						Iniatiation of						
RT2						RT2						
0	50	0	0	1.000	0.000	0	50	0	0	1.000	0.000	
1	50	13	3	0.729	0.064	1	50	1	3	0.979	0.021	
2	34	5	2	0.621	0.072	2	46	9	5	0.778	0.064	
3	27	5	4	0.500	0.081	3	32	3	5	0.704	0.077	
4	18	3	3	0.402	0.086	4	24	3	3	0.607	0.087	

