### **Stopping Rule for Necrosis:**

Necrosis will be monitored throughout the trial and accrual to the trial suspended at any time the following stopping criteria are met. Necrosis will be graded according to the CTCAE v4.0 terminology. If evidence develops that more than 20% of patients are expected to develop necrosis (CTCAE v4.0 > grade 3) the treatment will be considered unacceptable. The number of patients who experience necrosis is based upon the number of enrolled patients. The stopping criteria shown in the following table are based on exact lower 95% Blyth-Still-Casella confidence bounds.

> St. Jude Children's Research Hospital IRB NUMBER: Pro00004349

IRB Approval date: IRB APPROVAL DATE: 02/01/2023

Number of Patients	Number of Eligible	Exact 95% Lower
Experiencing Necrosis	Patients	Confidence Bounds
7	≤ 20	≥ 0.201
10	≤ 30	≥ 0.193
13	≤ 40	≥ 0.204
16	≤ 50	≥ 0.211
18	≤ 60	$\geq$ 0.204
20	≤ 70	≥ 0.202
23	≤ 80	≥ 0.211

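### Necrosis arising after progression has no provision for being recorded, yet the patient stays in the stopping-rule denominator, so the rule loses power to stop

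*Combined protocol and SAP*

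**What the plan says.** - **Stopping rule (11.1).** Accrual is suspended "If evidence develops that more than 20% of patients are expected to develop necrosis" at the stated grade. The boundaries are "based on exact lower 95% Blyth-Still-Casella confidence bounds": 7 cases in up to 20 patients, then 10/30, 13/40, 16/50, 18/60, 20/70 and 23/80. On the denominator: "The number of patients who experience necrosis is based upon the number of enrolled patients". The table column is headed eligible patients. Neither text nor table sets a follow-up or evaluability condition.
- **Necrosis (7.0).** Grading rests on serial MRI changes and symptoms. The rate is anticipated to lie in a range that "will be greater than 5% and less than 20% when estimated at one year".
- **Off study (8.1).** The list includes "Disease progression".
- **Follow-up (8.0).** "The survival for all participants will be followed on study until their death", unless the family declines. No other outcome is named.

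No section says whether necrosis is recorded after progression, or how a patient who progresses before 12 months is counted.

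**The concern.** A patient who progresses at month 4 leaves the study under 8.1. If necrosis develops at month 9, survival contact does not supply the serial imaging and symptom review on which grading depends. Because the denominator is everyone enrolled, that patient still counts as free of necrosis. The error runs one way, towards not stopping.

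Monitoring for excessive necrosis is part of the primary objective, and this is the trial's only toxicity stopping rule. Section 9.1.2.1 lists necrosis among the events not treated as serious or unexpected, so expedited reporting is a weak backstop. Section 7.0 also says that treatment effects can mimic progression on imaging, so a patient may be removed for apparent progression just when necrosis surveillance matters.

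**Working it through.** **1. The plan's own figures.** The lower limits of two-sided 90% Blyth-Still-Casella intervals (one-sided 95%) for the seven boundaries are 0.2015, 0.193, 0.204, 0.212, 0.2035, 0.2025 and 0.211. The printed values are 0.201, 0.193, 0.204, 0.211, 0.204, 0.202 and 0.211. They agree within 0.001, so the boundaries are as described. The question is what is fed into them.

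**2. Inputs.**
- One-year historical PFS (Table 11.1, row "1 50 13 3 0.729 0.064"): 0.729, so 27.1% fail in year 1. Failure there is a composite of relapse, progression, second malignancy or death.
- Constant hazard matching it: −ln(0.729) = 0.316 per year.
- Design hazard for the first four years (11.1): 0.233 per year, so 1 − exp(−0.233) = 20.8% fail in year 1.
- Assumed: necrosis independent of progression, with timing uniform over a stated window. The only related timing for conventional treatment is in section 2.1, for brainstem necrosis after first irradiation (under 8 months from the start). Section 2.5 cites imaging changes at 7–8 months in three hypofractionated patients.

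**3. Share of one-year necrosis that is observable.** This is the average of exp(−λt) over the necrosis window. The recorded rate is the true rate times this share.

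| Assumption | Share | True rate recorded as 20% |
|---|---|---|
| Months 0–12, λ = 0.316: (1 − e^−0.316)/0.316 | 0.857 | 23.3% |
| Months 6–12, λ = 0.316: (e^−0.158 − e^−0.316)/0.158 | 0.790 | 25.3% |
| Months 0–8, λ = 0.316 | 0.902 | 22.2% |
| Months 0–12, λ = 0.233 | 0.892 | 22.4% |
| Months 0–12, λ = 0.316, removal 3 months after progression | about 0.92 | 21.7% (0.20/0.92) |
| Bound: all necrosis in year-1 failures lost | 0.729 | 27.4% |

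**4. Chance of stopping, complete one-year data on every patient counted.** Exact binomial recursion over the printed boundaries, from n = 20 to n = 80:

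| True rate | No loss | 0.857 | 0.790 | 0.902 | 0.729 (bound) |
|---|---|---|---|---|---|
| 20% | 15% | 6% | 4% | 8% | 2% |
| 25% | 44% | 22% | 14% | 28% | 9% |
| 30% | 77% | 49% | 35% | 58% | 24% |
| 35% | 95% | 77% | 62% | 84% | 47% |
| 40% | 99% | 93% | 84% | 96% | 72% |

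**5. Chance of stopping, real-time monitoring against enrolled patients.** This is how the rule reads. Simulation of 90 patients entering at 11 per year (assumed, between the 12 planned and the roughly 10 reported at amendment 2), re-irradiation at entry, 4,000 trials. Recently enrolled patients with short follow-up lower the no-loss column too, which is a separate source of dilution.

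| True rate and timing | No loss at progression | Loss at progression |
|---|---|---|
| 25%, months 0–12 | about 27% | about 11% |
| 30%, months 0–12 | about 60% | about 32% (38% with λ = 0.233; 44% with a 3-month lag) |
| 35%, months 0–12 | about 87% | about 61% (74% with a 3-month lag) |
| 30%, months 6–12 | about 50% | about 13% |
| 35%, months 6–12 | about 81% | about 35% |

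Each loss figure must be read against the no-loss figure for the same timing. Comparing the months 6–12 losses with the months 0–12 baselines would overstate the effect.

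**The case against.** The strongest reply is that no section says necrosis recording stops at progression. Section 11.1 says necrosis is monitored throughout the trial, section 9.3 collects radiotherapy-related adverse events with no end date, and section 6.9.2 puts unscheduled imaging for toxicity or progression into the data set. Section 8.0 has patients followed on study to death. A reader might infer that such patients cannot be scored at all. The documents do not establish that. They establish that 8.0 and 11.1 pull against 8.1, and that nobody counting cases is told which governs. That part of the reply stands.

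A reader might also infer that 27% of necrosis goes unseen and that the rule cannot detect rates well above 20%. Neither follows. The 27% is historical composite failure, and only necrosis arising after removal is lost. Section 7.0 says progression should not rest on one imaging time point and describes confirmation 3–6 months later, so some patients stay observed longer. With complete data the rule still stops in 62–84% of trials at a true 35%, outside the worst-case bound.

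The rule is also weak for another reason: with no loss at progression it still misses a true 25% in 56% of trials, because it requires a lower bound near 20%.

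Finally, losses concentrate in the short-control anaplastic stratum (one-year PFS 0.476), but the documents give no link between that stratum and necrosis risk.

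These replies limit the size. None reverses the direction or supplies the missing instruction.

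**Conclusion.** The concern holds as a gap with a known direction and an uncertain size. Followed as written, the plan does not provide for necrosis arising after progression but keeps the patient in the denominator, so the recorded rate is too low and the rule loses power. At a true 30%, stopping falls from about 60% to about 32% in real time (38–44% under the milder variants), and from 77% to 49% with complete one-year data. If necrosis comes in months 6–12, the real-time fall is from about 50% to about 13%. These figures assume independence of necrosis and progression, a constant failure hazard, and necrosis timing that the documents do not give for fractionated re-irradiation.

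**What to change.** Reconcile 8.0, 8.1 and 11.1. State in each that CNS necrosis (grade and date) continues to be recorded after progression until 12 months after the start of re-irradiation, and that these events count in the stopping rule. Report the rule's operating characteristics under that follow-up.

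If recording after progression is impossible, replace the crude proportion with a time-to-event estimate at one year, and say which quantity the 20% limit refers to. Censoring at progression estimates the rate that would be seen without removal, assuming independence. Cumulative incidence with progression or death as a competing event estimates necrosis occurring first, which is a lower quantity. Section 11.2 already plans a competing-risk analysis for hearing loss.

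Dropping patients who leave early without necrosis from the denominator is a tempting shortcut, but it keeps early necrosis cases and biases the rate upward. With the months 0–12 assumptions, a true 20% becomes 0.1715/(1 − 0.8 × 0.271 − 0.2 × 0.143) = 22.7%. Real-time stopping at a true 20% rises from about 6% with no loss to about 15%.

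The cost is a short amendment that changes no treatment and builds on the survival contact already planned. The drawback is that attributing necrosis after progression and further therapy is harder, so the grading instructions should say how doubtful cases are counted.

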#### 3.3 Recruitment

The statistical design of this trial requires that 90 eligible patients be enrolled over a 9 year period. Accounting for ineligible patients, which are expected to be at most 10%, the total number of patients to be accrued to this study may be 99. We expect to enroll about 12 patients per year for approximately 9 years. The study will enroll patients with ependymoma and progressive disease. There is no exclusion to enrollment based on the time interval between initial tumor progression and enrollment. In the event that the accrual of patients is slower than expected, we will consider collaborating with other centers that specialize in the treatment of ependymoma. Patients with a prior history of radiosurgery may be excluded from protocol enrollment if the principal investigator or his designee determines that the risk of injury associated with fractionated retreatment is excessive.

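### The necrosis stopping table does not match its stated basis: one row triggers at a bound below 20%, and the printed column is not an exact 95% lower bound under either reading

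*Combined protocol and SAP*

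**What the plan says.** The rule is in the combined protocol and SAP, section 11.1, under Stopping Rule for Necrosis. The treatment is unacceptable "If evidence develops that more than 20% of patients are expected to develop necrosis" above the stated CTCAE grade. Necrosis is monitored throughout, with "accrual to the trial suspended at any time the following stopping criteria are met". On the basis of the counts: "The stopping criteria shown in the following table are based on exact lower 95% Blyth-Still-Casella confidence bounds". Whether 95% is one-sided or two-sided is not stated.

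The table has seven rows, each giving an event count, a maximum number of patients and a lower bound: 7/20 (0.201), 10/30 (0.193), 13/40 (0.204), 16/50 (0.211), 18/60 (0.204), 20/70 (0.202) and 23/80 (0.211). No overall chance of suspension is given.

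Two neighbouring statements matter. Section 3.3 says "The statistical design of this trial requires that 90 eligible patients be enrolled over a 9 year period", but the table ends at 80. The text of the rule says "The number of patients who experience necrosis is based upon the number of enrolled patients", while the column header counts eligible patients. Section 7.0 (Necrosis) expects a rate that "will be greater than 5% and less than 20% when estimated at one year".

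**The concern.** A reader comparing the table with its own description meets two problems. The first needs no calculation: a rule built on a lower bound above 20% contains a row whose printed bound is 0.193. The second appears on recalculation: the column is labelled as exact 95% lower bounds, but it is neither the lower end of 95% intervals nor a set of valid one-sided 95% bounds.

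Monitoring for excessive necrosis is written into the primary objective, and this table is the trial's toxicity boundary. If its counts do not carry the stated confidence, a monitoring committee cannot tell what evidence a crossing represents. At 20, 30 and 70 patients the table suspends on weaker evidence than an exact one-sided 95% bound would require.

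**Working it through.** **Inputs.** The 20% limit, the seven counts and the seven printed bounds come from the stopping rule in section 11.1.

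**Step 1: reproduce the printed column.** Blyth-Still-Casella limits start from Clopper-Pearson limits with α/2 in each tail. Each lower limit is then raised as far as possible while the interval's coverage stays at least 1−α for every true rate. This was done on a grid of 1/10000 with α = 0.10 and α = 0.05.

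**Step 2: one-sided check.** The exact one-sided 95% (Clopper-Pearson) lower bound is the rate p that solves P(X ≥ x | n, p) = 0.05, i.e. the 5% quantile of Beta(x, n−x+1). Because this tail rises with p, the bound is below 0.20 exactly when P(X ≥ x | n, 0.20) exceeds 0.05.

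| Row | Printed | BSC two-sided 90% | BSC two-sided 95% | One-sided exact 95% | P(X ≥ x) at 20% |
|---|---|---|---|---|---|
| 7/20 | 0.201 | 0.201 | 0.154 | 0.177 | 0.0867 |
| 10/30 | 0.193 | 0.193 | 0.175 | 0.193 | 0.0611 |
| 13/40 | 0.204 | 0.204 | 0.193 | 0.204 | 0.0432 |
| 16/50 | 0.211 | 0.212 | 0.201 | 0.212 | 0.0308 |
| 18/60 | 0.204 | 0.204 | 0.196 | 0.204 | 0.0427 |
| 20/70 | 0.202 | 0.202 | 0.189 | 0.198 | 0.0545 |
| 23/80 | 0.211 | 0.211 | 0.198 | 0.205 | 0.0388 |

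The two-sided 90% column reproduces the plan, with a difference of 0.001 at 16/50. The other columns do not.

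- Two-sided 95% reading: only 16/50 reaches 0.20.
- One-sided 95% reading: 7/20, 10/30 and 20/70 fail. A two-sided 90% Blyth-Still-Casella interval controls the two tails together and may put more than 5% in one of them. Here it does.
- 10/30: no bound tried exceeds 0.1933.

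**Step 3: counts that meet 20% at the existing row ends.**

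- One-sided exact 95%: 8/20 (0.217), 11/30 (0.221), 13/40, 16/50, 18/60, 21/70 (0.211), 23/80.
- Two-sided 90% Blyth-Still-Casella: only 10/30 changes, to 11/30 (0.221).

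**Step 4: overall chance of suspension by 80 patients.** An exact patient-by-patient binomial recursion was used, with each outcome taken as known at enrolment.

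| Boundary | True rate 20% | True rate 30% |
|---|---|---|
| Printed table | 14.9% | 76.7% |
| 11/30 corrected only | 14.0% | 76.1% |
| One-sided exact 95% at row ends | 9.7% | 72.3% |

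At a true rate of 40%, the mean number of patients is 21.5 for the printed table and 25.9 for the one-sided 95% counts, with trials that never suspend counted as 80.

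**Step 5: inside the blocks.** Each row applies the count for its last patient to every earlier patient. One-sided exact 95% bounds are 0.607 for 6/6, 0.222 for 5/10, 0.200 for 18/61 and 0.207 for 21/71. The table requires 7, 7, 20 and 23 events there, so none of these would suspend accrual. Per-patient one-sided counts starting at n = 5 would give 16.4% and 78.5% suspension at 20% and 30%. The mean number of patients would be 18.4 and 10.7 at 40% and 50%, against 21.5 and 14.5 for the printed table.

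**The case against.** The lower end of a two-sided 90% interval is commonly called a 95% lower bound. The plan names its method and does not promise 5% in each tail. By that method six of the seven rows exceed 0.20, and the tail excess at 20/70 is about half a percentage point. This stands as a defence of the counts, which is why keeping the method with a correct label is an acceptable fix. It does not rescue the 10/30 row, and it does not make the description as an exact 95% bound true.

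A reader might infer from the promise of suspension at any time that every crossing of 0.20 at any number of patients should suspend accrual, and that missing 6 of 6 is therefore an arithmetic error. The documents do not support that. The wording refers to the criteria in the table, and the table's maximum patient numbers and minimum bounds show a deliberately coarse block rule. Per-patient counts are a design option with a price. They raise the chance of suspension at a true 20% from 14.9% to 16.4% even when looks start at n = 5. Applied literally from the first patient, they would suspend at 2 of 2 (bound 0.224).

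Section 11.1 also reports 53 patients accrued by amendment 2, so the early rows mostly concern enrolment numbers already passed. That limits the practical effect, but 20/70 and the later rows lie beyond that number.

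**Conclusion.** The point holds for two matters. The 10/30 row contradicts the 20% limit on the page. The column is not an exact 95% lower bound: six of seven rows fall short of 0.20 on the two-sided 95% reading, and three of seven on the one-sided reading. The block structure is a secondary matter of design.

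A reader might conclude that the table is simply too easy to trigger, or simply too slow. Neither is supported. It needs less evidence than a one-sided 95% bound at 20, 30 and 70 patients, and more than that bound at many points inside the blocks.

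The overall effect is moderate. Correcting 10/30 alone changes the chance of suspension by less than one point at 20% (14.9% to 14.0%) and at 30% (76.7% to 76.1%). Moving to one-sided 95% counts lowers it by 5.2 points at 20% (14.9 − 9.7) and 4.4 points at 30% (76.7 − 72.3). These probabilities assume that outcomes are known at enrolment. Section 7.0 frames the necrosis rate at one year, so the stopping times shown are optimistic for every boundary.

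**What to change.** Keep the 20% limit. State the level and sidedness of the bound, and make every row satisfy the limit under it. Two consistent versions are:

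- exact one-sided 95% (Clopper-Pearson) bounds: 8/20, 11/30, 13/40, 16/50, 18/60, 21/70, 23/80;
- two-sided 90% Blyth-Still-Casella limits, labelled as such: the present table with 10/30 changed to 11/30.

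Report the chance of suspension at true rates of 20% and 30% for the version chosen. Extend the table from 80 to the 90 planned eligible patients, and reconcile enrolled with eligible as the denominator. If the sponsor prefers per-patient counts, the first look and the cumulative chance of suspension should be specified in advance.

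The cost is one table and a few sentences. The one-sided 95% counts also give up about 4 points of suspension probability at 30% and suspend later at high rates (mean 25.9 against 21.5 patients at 40%). The relabelled version costs almost nothing in operating characteristics, but 7/20 and 20/70 would then rest on less than one-sided 95% confidence, and the text should say so.
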